6.2 Interim analyses

The DMC will monitor the accumulating outcome data, and one of their roles is to recommend cessation of recruitment if a clear result has been reached (i.e. if either adrenaline or placebo is clearly superior). We suggest that different thresholds of evidence for early termination are adopted if adrenaline or placebo being more effective, as it is likely that stronger evidence would be needed to change current practice (adrenaline use) if placebo is found to be superior. We therefore propose that interim analyses are conducted frequently in the early stages of the trial, so that, if adrenaline is superior, this can be detected early. Thus we will minimise any risks to patients while producing robust evidence that will change practice.

The outcomes of primary interest for interim analyses are 30 day survival and neurological status. We propose to prepare reports for the DMC initially on a three monthly basis. The exact schedule of interim analyses and the nature of any early stopping rules will be determined by the DMC, in discussion with the investigators, before the start of recruitment.

6.3 Economic Evaluation

An economic evaluation will be integrated into the trial design. The economic evaluation will be conducted from the recommended NHS and personal social services (PSS) perspective (48). Data will be collected on the health and social service resources used in the treatment of each trial participant during the period between randomisation and six months post-randomisation. Resource utilisation data will be collected through four principal means: (i) use of trial interventions, concurrent treatments, mode and distance of initial transportation and subsequent transfers, will be estimated using the computerised data collection systems developed for the PARAMEDIC trial; (ii) detailed information on ITU resource utilisation and specific treatments (e.g. cardiovascular support, therapeutic hypothermia use) will be collected using bespoke trial data collection forms; this information will in turn be validated, and where necessary complemented, using information

collected from the Intensive Care Research National Audit Programme; (iii) information on subsequent hospital inpatient and day case admissions and outpatient visits will be collected through Hospital Episode Statistics; and (iv) trial participants or, where necessary, appropriate proxies will be asked to complete economic questionnaires profiling hospital readmissions and post-discharge health and social community care resource use at each time point of follow-up. For the purposes of a sensitivity analysis that will replicate the economic evaluation from a societal perspective, out-of-pocket expenses, and costs associated with lost productivity will also be measured in the economic questionnaires. Current UK unit costs will be applied to each resource item to value total resource use in each arm of the trial. A per diem cost for each level of hospital care, delineated by level of intensity, will primarily be calculated using national tariffs. However, primary research that uses established accounting methods may also be required to estimate costs unique to this trial. This may entail obtaining costs from NHS finance departments and apportioning these to different categories of patient using a 'top-down' methodology. Trial participating centres will be visited to ensure consistency in cost apportionments. The unit costs of community health and social services will largely be derived from national sources(49), although some calculations from first principles using established accounting methods may also be required]. Trial participants or, where necessary, appropriate proxies will be asked to complete the EuroQol EQ-5D-5L(50) and SF-12(51) measures at each time point of follow-up. In addition, health-related quality of life immediately prior to the critical illness will be retrospectively recalled at three months post-randomisation using the EQ-5D-5L and SF-12 by the trial participants themselves or, where necessary, appropriate proxies(52). Responses to the EQ-5D-5L and SF-12 will be converted into multi-attribute utility scores using established algorithms(53, 54).

An incremental cost-effectiveness analysis will be performed and expressed in the following terms: (i) incremental cost per additional survivor to 30 days post-cardiac arrest; (ii) incremental cost per additional neurologically-intact (mRS) survivor; and (iii) incremental cost per quality-adjusted life year (QALY) gained. Results will be presented using incremental cost-effectiveness ratios (ICERs) and cost-effectiveness acceptability curves (CEACs) generated via non-parametric bootstrapping. This accommodates sampling (or stochastic) uncertainty and varying levels of willingness to pay for an additional QALY. Heterogeneity in the trial population will be explored by formulating a net-benefit value for each patient from the observed costs and effects, and then constructing a regression model with a treatment variable and covariates such as age, gender, duration of OHCA and study site. The magnitude and significance of the coefficients on the interaction between the covariates and the treatment variable should provide an estimate of the cost-effectiveness of adrenaline by sub-group. Due to the known limitations of within-trial economic evaluations(55) we will also construct a decision-analytical model to model beyond the parameters of the proposed trial the cost-effectiveness of adrenaline in this clinical population. Survival analysis models will be used to estimate life expectancy with and without adrenaline beyond the time horizon of the trial. Long term costs and health consequences will be discounted to present values using discount rates recommended for health technology appraisal in the United Kingdom. A series of probabilistic sensitivity analyses will be undertaken to explore the implications of parameter uncertainty on the incremental cost-effectiveness ratios.

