1.1.2.2 Cardiovascular toxicity

In a further analysis of the Norwegian IV versus no IV trial(10), adrenaline increased the frequency of transitions from PEA to ROSC and extended the time window for ROSC but at a cost of greater cardiovascular instability after ROSC, with a higher rate of re-arresting. These observations are consistent with other studies which link adrenaline with ventricular arrhythmias and increased post-ROSC myocardial dysfunction (21). In human studies with patients with sepsis (22) or acute lung injury (23), β agonist stimulation is similarly linked to cardiovascular instability and reduced survival (24). A systematic review of β blocker treatment in animal models of cardiac arrest found fewer shocks were required for defibrillation, myocardial oxygen demand was reduced and post resuscitation myocardial stability improved with less arrhythmia and improved survival(25).

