2. TRIAL DESIGN

2.1 Trial summary

This is a pragmatic, individually randomised, double blind, controlled trial and economic evaluation.

[figure not shown]
Patients will be eligible if they are in cardiac arrest in the out-of-hospital environment and advanced life support is initiated. Exclusions are cardiac arrest as a result of anaphylaxis or life threatening asthma, patient known or appears to be under 16 and known or apparent pregnancy.

Patients will be randomised to either adrenaline (intervention) or placebo (control). Randomisation will occur when the trial IMP pack has been opened.

Outcomes are survival to 30 days (primary outcome), survival to hospital discharge, 3, 6 and 12 months, health related quality of life, health economics, neurological and cognitive outcomes (secondary outcomes).

All survivors will be contacted and invited to take part in the follow up (at 3 and 6 months).

Figure 3. Flow chart for PARAMEDIC-2 trial

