2.6.8 What should the patient or legal representative be asked later?

We will seek consent to continue in the trial. Our rationale is that the patient will be enrolled in the trial at the time of their cardiac arrest if they meet the eligibility criteria. The duration of the research intervention (adrenaline or placebo) will typically last for 5-20 minutes and rarely more than 45 minutes. Adrenaline is rapidly metabolised by the body after administration with a half-life duration of 5-10 minutes (time it takes for the body to remove half the drug). The intervention phase of the trial will therefore be complete within an hour of the patient sustaining a cardiac arrest.

We will approach patients or their legal representative, as soon as practicable after the initial emergency has passed to inform them of their participation and request consent to continue using the steps outlined below.

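### Section 6.3 uses duration of OHCA as covariate and subgroup factor in the net-benefit regression; the term is undefined and, read naturally, is a post-randomisation variable that adrenaline changes

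*Protocol*

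**What the plan says.** Section 6.3 sets out a secondary economic model: "Heterogeneity in the trial population will be explored by formulating a net-benefit value for each patient", followed by "constructing a regression model with a treatment variable and covariates such as age, gender, duration of OHCA and study site". It then says how the output will be read: "the interaction between the covariates and the treatment variable should provide an estimate of the cost-effectiveness of adrenaline by sub-group". Arrest duration is therefore named both as an adjustment variable and as a factor whose interaction with treatment will be interpreted.

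The main economic output is separate: "Results will be presented using incremental cost-effectiveness ratios (ICERs) and cost-effectiveness acceptability curves (CEACs) generated via non-parametric bootstrapping". No covariates are stated for it.

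Three other places bear on when arrest duration is settled and what influences it:

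- Section 2.1: "Randomisation will occur when the trial IMP pack has been opened".
- Section 2.6.8: "The duration of the research intervention (adrenaline or placebo) will typically last for 5-20 minutes and rarely more than 45 minutes".
- Section 1.1.2.2, on the Norwegian trial: "adrenaline increased the frequency of transitions from PEA to ROSC and extended the time window for ROSC".

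The protocol does not define duration of OHCA. Its only other use is in Section 1.1.1, in the list of adjustment variables of a North American registry analysis. There it stands beside the time from emergency call to ambulance arrival, as a separate item.

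**The concern.** A covariate or subgroup factor in a randomised comparison should be fixed before allocation, or at least be unaffected by it. If duration runs to ROSC or termination, it is neither.

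- **It lies on the path from treatment to outcome.** Adrenaline changes ROSC, ROSC ends the arrest, and survival and costs follow. Adjusting for duration removes part of the effect being estimated.
- **It is a common effect of treatment and of unmeasured prognosis.** Patients with a better outlook regain circulation sooner. Among patients with equal duration, the two arms no longer have the same prognosis.
- **Subgroups of it are partly made by the treatment.** The short arrests on adrenaline are not the counterpart of the short arrests on placebo.

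The result at stake is a statement that adrenaline is more, or less, cost-effective in long or short arrests. Such a pattern could arise from the conditioning alone. Nor could it guide practice, because the total duration is unknown when the pack is opened.

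**Working it through.** **1. Timing.** Randomisation is pack opening (Section 2.1), during an arrest still in progress. Treatment then typically runs 5-20 minutes (Section 2.6.8). The end of the arrest, by ROSC or termination, therefore follows randomisation.

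**2. Does treatment change it?** Section 1.1.1 gives the counts; odds ratio = ad/(bc), with a Woolf 95% interval.

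- Placebo-controlled trial, ROSC 64/272 against 22/262: (64 × 240)/(208 × 22) = 3.36. SE of log OR = √(1/64 + 1/208 + 1/22 + 1/240) = 0.265. Interval 2.00 to 5.64. The protocol states 3.4 (2.0 to 5.6): reproduced.
- IV against no-IV trial, ROSC 165/418 against 107/433: (165 × 326)/(253 × 107) = 1.99, interval 1.48 to 2.66. The protocol states 1.99 (1.48 to 2.67): reproduced but for rounding.

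With the longer window for ROSC in Section 1.1.2.2, the protocol's evidence is that adrenaline alters both whether and when the arrest ends in ROSC.

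**3. Is it prognostic?** Section 2.6.1 says that treatment usually continues for up to 20 minutes and that survival is very unlikely after that. So duration is linked to both allocation and outcome.

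**4. What conditioning on it does (illustration).** The documents do not supply the inputs for a bias calculation, so all of the following are assumptions:

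- time to pack opening t0: gamma, mean 18 min;
- ROSC hazard per minute: 0.0035 × exp(βT + 0.8U − 0.02(t0 − 18)), with T the arm and U an unmeasured standard normal prognostic factor;
- termination about 25 min after pack opening (SD 6, limits 8 and 45), plus w minutes on adrenaline;
- duration = t0 + the earlier of ROSC and termination;
- logit of survival after ROSC: −1.2 + 0.8U − 0.04(t0 − 18) + δT;
- net benefit = 20,000 × 0.35 per survivor − (500 + 1,000 per ROSC + 2,000 per survivor).

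There were 2,000,000 simulated patients per scenario, analysed by ordinary least squares. Scenarios: (a) β = 1.25, w = 0, δ = 0; (b) β = 1.25, w = 0, δ = −1.05; (c) β = 1.05, w = 5, δ = −0.9. ROSC was about 30% against 10.9%, an odds ratio near 3.5 in each.

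Treatment coefficient, no interaction term:

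| Scenario | Outcome | Unadjusted | Adjusted for t0 | Adjusted for duration |
|---|---|---|---|---|
| (a) | survival, points | 6.57 | 6.57 | 4.56 |
| (a) | net benefit | 134 | 134 | 83 |
| (b) | survival, points | 1.23 | 1.23 | −0.11 |
| (b) | net benefit | −133 | −133 | −150 |
| (c) | survival, points | 1.81 | 1.81 | 2.45 |
| (c) | net benefit | −101 | −101 | −92 |

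Check on (a): each survivor adds 7,000 − 2,000 = 5,000, so 0.0657 × 5,000 − 0.194 × 1,000 = 134.

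Net-benefit interaction with treatment, per 10 minutes:

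| Scenario | With t0 | With duration |
|---|---|---|
| (a) | −77 | −93 |
| (b) | −2 | +111 |
| (c) | −12 | +91 |

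With a drug that does nothing, both adjustments gave a treatment coefficient of about 0.7 on net benefit and interactions of +2 (t0) and −0.5 (duration): zero within simulation error. The −2 in (b) is therefore also effectively zero.

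Adjusting for time before pack opening left the randomised contrast intact. Adjusting for total duration moved it whenever adrenaline affected ROSC: net benefit fell in (a) and (b) and rose in (c). The two interaction columns concern different modifiers and need not agree. What they show is that the duration interaction can be large and positive where modification by a true baseline interval is absent (b) or slightly negative (c).

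**The case against.** **The term is undefined.** If it meant collapse or emergency call to pack opening, it would be a baseline variable and the bias would disappear. A reader might infer from Section 6.3 that the model is certainly biased; the documents do not go that far. But nothing limits the term to time before pack opening, and the list in Section 1.1.1 separates it from response time. Section 6.1 names a call-to-drug interval when it wants one. The whole-arrest reading is the natural one, though not proven.

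**The list is illustrative and the model exploratory.** Both are true. The covariates are introduced as examples, and details may be settled in an analysis plan not shown here. Still, the protocol names this variable and says how its interaction will be read, so the choice is on the page.

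**The affected output is narrow.** This stands. A reader might infer that the trial's cost-effectiveness result or its primary result is compromised. Neither is: the ratios and acceptability curves come from bootstrapping with no stated covariates, and arrest duration is not among the effect modifiers in Section 6.1. Section 6.3 also interprets only the interactions, so bias in the adjusted treatment coefficient matters less.

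**A single figure for the bias is tempting but unsupported.** One could assume that adrenaline shortens every arrest by some minutes. A mean of 6 minutes across the arm, acting through ROSC, would need 6/0.235 = 25.5 minutes for each adrenaline patient with ROSC, or 6/0.151 = 39.7 minutes for each additional ROSC. The intervention itself typically lasts 5-20 minutes, and a longer window for ROSC argues against uniform shortening.

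**Conclusion.** The point holds in limited form. On its natural reading, duration of OHCA is completed after randomisation and affected by treatment on the protocol's own evidence. Using it as covariate or interaction factor would bias the treatment-by-duration interaction that Section 6.3 reads as subgroup cost-effectiveness, and also the adjusted treatment coefficient.

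The conclusion rests on two conditions: that the term covers the whole arrest, and that adrenaline affects ROSC in this trial as in the cited ones. If either fails, so does the concern. The documents do not give the direction or size; the simulated values show only that the bias can be material and can go either way. The consequence is confined to the exploratory heterogeneity regression.

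**What to change.** In Section 6.3, replace duration of OHCA with an interval that ends no later than pack opening, such as 999 call to ambulance arrival or 999 call to pack opening. Alternatively, keep the term and define it as ending at pack opening. Add one sentence restricting covariates and subgroup factors in this regression to variables fixed before randomisation; age, gender and study site already qualify.

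The cost is a phrase and a sentence. The 999-call time is already needed for the call-to-administration modifier in Section 6.1. The protocol does not list ambulance arrival or pack-opening times as data items, so confirm which of them is captured before choosing the interval.

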2.4.2 Sample size

The target sample size will be 8,000, which is expected to give a width of the 95% CI for the risk ratio of approximately 0.4 or slightly less; for a risk ratio of 1.25 the 95% CI is 1.07 to 1.46, and for risk ratio of 1.0 it is 0.84 to 1.19. There is a trade-off between precision and practicality in setting a target sample size; above 8,000, there is only a small improvement in precision, but the difficulty and time needed to recruit this number increase significantly. We expect a very small amount of missing data for survival outcomes; in PARAMEDIC we have ascertained survival status for over 99% of randomised patients, and we have therefore not adjusted the sample size estimates to account for missing data.

Using a conventional sample size calculation based on a significance test, a sample size of 8,000 would have 93% power to achieve a statistically significant ($p < 0.05$) result if the true treatment difference is a risk ratio of 1.33 (increase from 6% in adrenaline group to 8% in placebo group), or 75% power if the true treatment difference is a risk ratio of 1.25 (increase from 6% to 7.5%).

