6. ANALYSIS

6.1 Statistical analysis

The primary analysis will be by intention to treat, comparing the outcomes between all participants randomised to adrenaline and all those randomised to placebo. The focus of the analysis will be on estimation of treatment effects and the uncertainty around them. A detailed statistical analysis plan will be developed by the trial statisticians and approved by the TSC and DMC.

Results will be presented as estimates of the treatment effect with 95% confidence intervals. Dichotomous outcomes (survival to 30 days, survived event, and survival to hospital discharge, 3, 6 and 12 months) will be analysed using logistic regression models, both unadjusted and adjusted for appropriate covariates. Survival and other time to event outcomes such as duration of hospital and ICU stay will be analysed using time to event techniques. Continuous outcomes (quality of life, cognition, anxiety/depression, posttraumatic stress) will be analysed by regression methods and the results presented as the difference in means between the groups and 95% confidence intervals. Modified Rankin Scale (a 7 category ordinal variable) will be analysed by ordinal logistic regression and the results will be presented using odds ratios and 95% confidence intervals. This will provide an increase in power over using a dichotomous outcome variable. Reporting of analyses will follow CONSORT guidelines.

The following exploratory analyses will be used to investigate potential modifiers of the treatment effect of adrenaline:

- Age
- Witnessed cardiac arrest versus not witnessed

- Bystander CPR versus no bystander CPR
- Type of initial rhythm (VF/VT, PEA, Asystole)
- Time of 999 call to administration of adrenaline
- Aetiology of cardiac arrest (presumed cardiac versus non-cardiac).

For categorical subgrouping variables we will fit interaction terms in logistic regression models to estimate the difference in treatment effects between the subgroups and the uncertainty around this. For continuous variables, we will fit the treatment-modifying factor as a covariate in regression models.

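### Section 6.3 reads subgroup cost-effectiveness from treatment-by-covariate interaction coefficients, which show only how cost-effectiveness differs between subgroups

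*Protocol*

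**What the plan says.** Protocol section 6.3 (Economic Evaluation) sets out the subgroup part of the economic analysis in two sentences. The first gives the purpose and the model: "Heterogeneity in the trial population will be explored by formulating a net-benefit value for each patient from the observed costs and effects", followed by "constructing a regression model with a treatment variable and covariates such as age, gender, duration of OHCA and study site". The second says how the fit is to be read: "The magnitude and significance of the coefficients on the interaction between the covariates and the treatment variable should provide an estimate of the cost-effectiveness of" the trial drug in each subgroup.

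The section names no other quantity for subgroups. The incremental cost-effectiveness ratios (ICERs) and acceptability curves (CEACs), obtained by non-parametric bootstrap, are described without reference to subgroups.

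Section 6.1 (Statistical analysis) uses the same kind of term for the clinical outcomes. For categorical subgrouping variables the plan there is to "fit interaction terms in logistic regression models to estimate the difference in treatment effects between the subgroups and the uncertainty around this".

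**The concern.** The two sections give the same kind of coefficient two different meanings. In section 6.1 an interaction measures how far the treatment effect differs between subgroups. In section 6.3 its size and significance are said to estimate cost-effectiveness within subgroups. Only the first is right.

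Whether adrenaline is cost-effective in a subgroup depends on whether incremental net benefit there is above or below zero at a given willingness to pay. A difference between two subgroups does not fix the level in either. An analyst or reader who took the sentence at its word would draw subgroup conclusions from a number that cannot carry them.

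**Working it through.** The plan gives no figure on this point, so there is none to reproduce. The argument is algebraic, and the numbers only illustrate it.

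**Algebra.** Let a patient's net benefit be NB = λ × effect − cost, where λ is the willingness to pay. For treatment T (1 = adrenaline, 0 = placebo) and a binary covariate X:

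NB = a + b·T + c·X + d·T·X

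- Incremental net benefit (INB) at X=0 is b.
- INB at X=1 is b + d.
- Hence d = INB(X=1) − INB(X=0).

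Adding the same constant to both INBs leaves d unchanged, so d says nothing about the sign or size of either. Its null hypothesis is that the two INBs are equal. The null for cost-effectiveness in a subgroup is that INB there is zero.

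The same holds for the other covariates named in section 6.3. If age is entered linearly, d is the change in INB per year of age, and INB at age x is b + d·x. For study site, each interaction coefficient also depends on which site is the reference, whereas a site's own INB does not.

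**Inputs for the illustration.**

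- Total sample size, from section 2.4.2: "The target sample size will be 8,000".
- Assumed: 1:1 allocation and two equal subgroups, so 2,000 patients per arm in each subgroup.
- Assumed: SD of net benefit 10,000 in arbitrary money units, since the protocol gives none. Values of 5,000 and 20,000 were also tried.

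**Standard errors at SD 10,000.**

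- INB in one subgroup: 10,000 × √(2/2,000) = 316, so the 95% CI is the estimate ± 1.96 × 316 = ± 620.
- Interaction: 316 × √2 = 447, so the 95% CI is the estimate ± 1.96 × 447 = ± 877 (unrounded SE).

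**Four cases.**

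| Case | INB at X=0 | INB at X=1 | Interaction d | z = d/447 | p for d | Cost-effective in |
|---|---|---|---|---|---|---|
| A | +1,000 | +2,500 | +1,500 | 3.35 | 0.0008 | both |
| B | −2,500 | −1,000 | +1,500 | 3.35 | 0.0008 | neither |
| C | −1,500 | −1,400 | +100 | 0.22 | 0.82 | neither |
| D | +1,500 | +1,400 | −100 | −0.22 | 0.82 | both |

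Every subgroup INB in the table is clear of zero. The smallest in absolute size is 1,000, with z = 1,000/316 = 3.16 and p = 0.0016. Yet A and B have the same interaction and p-value with opposite conclusions, and so in effect do C and D.

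Fitting the regression to constructed data with cell means matching cases A, B and C gave the same estimates and p-values to rounding. At SD 5,000 and 20,000 the p-values are the same when the effects are scaled with the SD. With other effects or subgroup shares the p-values would change, but the algebra would not.

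**The case against.** The strongest reply is that the disputed sentence should be read with the one before it, which sets the aim as exploring heterogeneity. For that aim the interaction is the right quantity, and the sentence may simply mean how cost-effectiveness varies across subgroups. The model already contains the treatment variable, so the subgroup INB can be had from the same fit. Section 6.1 shows that the team understands interaction terms. The wording is soft, and tabulating subgroup net benefit in detail is normal matter for an analysis plan.

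Most of this stands and limits the weight of the point. It does not remove it. The sentence goes beyond heterogeneity: it claims an estimate of cost-effectiveness by subgroup, names the interaction's magnitude and significance as the basis, and mentions neither the treatment coefficient nor any other subgroup quantity. That is an interpretation the protocol states, and states wrongly. It is not a detail left for later.

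A reader might infer more: that a uniform benefit will be reported as no cost-effectiveness by subgroup, or that a subgroup with zero net benefit will be declared cost-ineffective because the reference group benefits. The documents do not support this. Section 6.3 attaches no decision rule to the interaction p-value, and the treatment coefficient and the overall ICER and CEAC would be available beside it. Nor is it fair to describe the interaction test as having lost power or an inflated error rate. It is a valid test of its own null, and it only looks faulty when set against a different one.

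**Conclusion.** The point holds as an error of stated interpretation. The interaction coefficients estimate differences in incremental net benefit between subgroups, and subgroup cost-effectiveness cannot be read from them alone. This follows from the form of the model and rests on no assumed figure. The assumed SD, allocation and equal subgroups affect only the illustration, in which an interaction of +1,500 with p=0.0008 fits adrenaline being cost-effective in both subgroups or in neither.

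The reach is limited. Cost-effectiveness is a secondary objective (section 2.2.2), and this is an exploratory part of it. The regression itself is sound. The overall ICER and CEAC, the primary outcome and the sample size are untouched. The sentence should be corrected, but the design is not in question.

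**What to change.** Replace the sentence in section 6.3, or correct it in the health economics analysis plan, along these lines:

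> Treatment-by-covariate interaction coefficients, with 95% confidence intervals, will be used only to assess whether cost-effectiveness differs between subgroups. Cost-effectiveness in each subgroup will be estimated as the incremental net benefit there (the treatment coefficient plus the relevant interaction coefficient, or the value at chosen levels of a continuous covariate such as age), with a 95% confidence interval from the joint covariance of the coefficients or from the bootstrap, at stated willingness-to-pay values.

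If several interactions are fitted in one model, the text should also say at what values the other interacting covariates are held, or that INB is averaged over the patients in the subgroup.

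The cost is one sentence and one linear combination per subgroup, from the same model and data and with the bootstrap already planned. The small downside is wide subgroup intervals. In the illustration, the SE for the whole trial would be 10,000 × √(2/4,000) = 224 against 316 for a subgroup of half the patients, so the interval is about 1.4 times as wide, and smaller subgroups would fare worse. That width is a fair picture of what the data can show.
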